7.1.3. ADVERSE EVENTS

Solicited Adverse Events:

Daily recording of solicited adverse events: for diary cards indicating the presence or absence of solicited adverse events, for studies using paper diaries which have questions in the CRF indicating the presence or absence of solicited events the following rules are applicable:

Document: \\dccar2dnetvnasc01p-lan1.quintiles.net\cp_ops\PROJECTS\Glaxo SmithKline\GSK216152_WZA10802\SAP
Author: PPD Version Number: 2.0
Version Date: 07DEC2023

Template No: CS_TP_BS016 – Revision 7
Effective Date: 01Nov2021

Reference: CS_WI_BS005

- Denominators for the summary of administration site (or systemic) solicited adverse events will be calculated using the number of participants who respond "Yes" or "No" to the question concerning the occurrence of administration site (or systemic) adverse events.
- When a specific solicited adverse event is marked as having not occurred following a specific vaccination (i.e., SDTM FA.FAOCCUR=N for the specified post-vaccination period for the adverse event in question), all daily measurements will be presented as missing.
- When a specific solicited adverse event is marked as having occurred following a specific vaccination (i.e. SDTM FA.FAOCCUR=Y for the specified post-vaccination period for the adverse event in question), any missing daily recordings will be given imputed values to allow them to contribute to the 'Any' rows but not to specific grade rows of the solicited adverse event summary tables.
- When the occurrence of a specific solicited adverse event is not present (i.e. SDTM FA.FAOCCUR is neither Y nor N for the specified post-vaccination period for the symptom in question) but the group of solicited adverse events (administration site or systemic) is marked as having occurred (i.e. SDTM FA.FAOCCUR=Y), all missing daily recordings will be given imputed values to allow them to contribute to the 'Any' rows but not to specific grade rows of the solicited adverse event summary tables.

The following table shows how participants contribute to each category for a specific solicited adverse event over the Day X to Day Y post-vaccination period:

Solicited adverse event category	Participants included in the calculation of the numerator
Any	All participants with at least one occurrence of the adverse event at grade 1, grade 2, or grade 3 between Day X and Day Y or with the adverse event marked as present and at least one missing daily recording between Day X and Day Y

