7.2.6. COUNTING RULES FOR OCCURRENCES OF SOLICITED ADVERSE EVENTS

When the occurrences of solicited adverse events are summarized, each event recorded as having occurred during a specific period will be counted as only one occurrence regardless of the number of days on which it occurs.

For a given participant and the analysis of solicited symptoms within 7 days post-vaccination, missing or non-evaluable measurements will not be replaced. Therefore, the analysis of the solicited adverse events will include only vaccinated participants for doses with documented safety data (i.e., diary card completed). A diary card is considered complete when it has data recorded for all 7 days post vaccination. More specifically the following rules will be used:

- Participants who documented the absence of a solicited symptom after one dose will be considered not having that symptom after that dose.
- Participants who documented the presence of a solicited symptom and fully or partially recorded daily measurement over the solicited period will be included in the summaries at that dose and classified according to their maximum observed daily recording over the solicited period.
- Participants who documented the presence of a solicited symptom after one dose without having recorded any daily measurement will be assigned the value 'UNKNOWN'.
- Doses without diary cards returned will be excluded.

The following table describes the rules in detail to be followed in various possible scenarios:

Solicited Symptom	Occurred?	Daily Measurement Record (D1-D7) Missing?	Grade of non-missing values	Maximum Grade for Summary Tables	Contribute to 'Any' row in Summary Tables
All administration site/systemic AEs	No (as per CRF)	Fully Missing	NA	NA	No
All administration site/ systemic AEs (except Temperature)	Yes (as per CRF)	Fully Missing	NA	UNKNOWN	Yes
	Yes (as per CRF)	Partially Missing	All 0s	UNKNOWN	Yes

Document: \\dccar2dnetvnasc01p-lan1.quintiles.net\cp_ops\PROJECTS\Glaxo SmithKline\GSK216152_WZA10802\SAP
 Author: PPD Version Number: 2.0
 Version Date: 07DEC2023

Template No: CS_TP_BS016 – Revision 7
 Effective Date: 01Nov2021

Reference: CS_WI_BS005

Solicited Symptom	Occurred?	Daily Measurement Record (D1-D7) Missing?	Grade of non-missing values	Maximum Grade for Summary Tables	Contribute to 'Any' row in Summary Tables
	Yes (as per CRF)	Partially Missing	At least one grade $\neq 0$	Maximum grade of non-missing values	Yes

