Temperature	Missing (computed variable if value $\geq 38.0^{\circ}\text{C}$)	Fully Missing	NA	UNKNOWN	Yes
	Missing (computed variable if value $\geq 38.0^{\circ}\text{C}$)	Partially Missing	All values $< 38.0^{\circ}\text{C}$	UNKNOWN	Yes
	Yes (computed variable if value $\geq 38.0^{\circ}\text{C}$)	Partially Missing	At least one value $\geq 38.0^{\circ}\text{C}$	Maximum grade of non-missing values	Yes

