16.1. ADVERSE EVENTS

The analysis of solicited adverse event will be performed in the Solicited Safety Set. The percentage of participants with at least 1 administration site AE (solicited and unsolicited), with at least 1 systemic AE (solicited and unsolicited) and with any AE during the 7-day or the 28-day follow-up period, for each stage, will be tabulated with exact 95% CI after each vaccination and overall. The same calculations will be performed for symptoms rated as grade 3 (severe). This combined analysis of solicited and unsolicited AEs will be performed on the Exposed Set as requested for public disclosure. Solicited

Document: \\dccar2dnetvnasc01p-lan1.quintiles.net\cp_ops\PROJECTS\Glaxo SmithKline\GSK216152_WZA10802\SAP
 Author: PPD Version Number: 2.0
 Version Date: 07DEC2023

Template No: CS_TP_BS016 – Revision 7
 Effective Date: 01Nov2021

Reference: CS_WI_BS005

events and unsolicited AEs will be coded by MedDRA.

The percentage of doses followed by at least 1 administration site AE and by at least 1 systemic AE will be tabulated, overall vaccination course, with exact 95% CI. The same computations will be done for Grade 3 AEs, any unsolicited AEs considered related to vaccination, any Grade 3 unsolicited AEs considered related to vaccination and any AEs resulting in a medically attended visit.

The percentage of participants/doses reporting each individual solicited administration site and systemic AE during the 7-day follow-up period will be tabulated with exact 95% CI as follows:

- Over the 3 doses, the percentage of participants with the symptom and its exact 95% CI.
- Over the 3 doses, the percentage of doses with the symptom and its exact 95% CI.
- At each study dose (visit), the percentage of participants with the symptom and its exact 95% CI.

Occurrence of fever within 7 days post vaccination will be reported per grade, per 0.5°C cumulative increments classes as from $\geq 38^{\circ}\text{C}$ as well as the occurrence of fever $>40^{\circ}\text{C}/104^{\circ}\text{F}$.

Solicited events ongoing after the observation period reported by maximum intensity will be left out of summary tables and only reported in solicited AE listings. Any solicited event with onset day greater than solicited period (i.e., 7 days) will be reported as unsolicited AE and will be included in unsolicited summary tables and listings.

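### SAP 7.2.6 counts a participant as having any fever when temperature readings are missing, none reached 38.0°C and fever is not marked as present

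*SAP*

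**What the plan says.** The table in SAP 7.2.6 has three Temperature rows. Fever is a computed flag, set when a value of at least 38.0°C exists. In two rows the flag is missing: one for fully missing readings, one for partly missing readings with every recorded value below the threshold ("All values $< 38.0^{\circ}\text{C"). Both give maximum grade UNKNOWN and contribute to 'Any'. The third row has at least one value of 38.0°C or more and takes the highest observed grade.

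The surrounding text says other things:

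- SAP 7.2.6, on when UNKNOWN is given: "Participants who documented the presence of a solicited symptom after one dose without having recorded any daily measurement will be assigned the value". Presence has to be documented first.
- SAP 7.2.6, on missing values: "missing or non-evaluable measurements will not be replaced".
- SAP 7.2.6, on diaries: "A diary card is considered complete when it has data recorded for all 7 days post vaccination". Doses with no returned diary are excluded.
- SAP 7.1.3, 'Any' numerator: an observed grade 1 to 3, or a participant "with the adverse event marked as present and at least one missing daily recording".
- SAP 7.1.3, last bullet: missing days may count in 'Any' when the specific flag is neither Y nor N "but the group of solicited adverse events (administration site or systemic) is marked as having occurred".
- SAP 7.1.3, denominator (either answer to the group-level question counts): "Denominators for the summary of administration site (or systemic) solicited adverse events will be calculated using the number of participants who respond".
- SAP 16.1.3: fever is a temperature of at least 38.0°C, and anything lower is grade 0.
- Protocol 9.5: no imputation of missing data.

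**The concern.** A missing flag is not a report of fever. Under the two rows, an incomplete temperature record becomes a fever case even if everything recorded was normal. For all other symptoms the same table asks for a CRF Yes before an UNKNOWN grade counts.

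Individual solicited systemic events, fever included, are part of the primary safety analysis (Protocol Table 11) in both stages. The 'Any' fever line could exceed the 38.0°C-and-above class in the same report, with no event to explain the gap. Two programmers, one working from 7.1.3 and one from 7.2.6, would get different fever counts from the same data. SAP 16.1 also asks for this line: "Over the 3 doses, the percentage of participants with the symptom and its exact 95% CI". That line rests on 3 × 7 = 21 evening readings, and one gap is enough to enter it.

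**Working it through.** The plan gives no figure to reproduce. The check compares the rules case by case, then sizes the effect of one misclassified participant.

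**Does the participant enter 'Any' fever?** The fever flag is treated as computed: Yes if a value of at least 38.0°C exists, otherwise missing.

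| Temperature record | Systemic group question | 7.2.6 rows | 7.1.3 numerator table | 7.1.3 last bullet |
|---|---|---|---|---|
| Fully missing | Y | Yes | No | Yes |
| Fully missing | N | Yes | No | No |
| One day missing, rest below 38.0°C | Y | Yes | No | Yes |
| One day missing, rest below 38.0°C | N | Yes | No | No |
| Complete, all below 38.0°C | Y or N | No | No | No |
| One day missing, one value of at least 38.0°C | Y or N | Yes | Yes | Yes |

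The rules disagree only for incomplete records without an observed fever. The 7.1.3 numerator never admits these. The last bullet admits them only if the systemic group is Y, a condition that 7.2.6 does not state. Even with that condition, a headache plus one missed evening reading becomes a fever case.

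**Size per affected participant.** One participant adds 100/n percentage points. Group sizes are from Protocol Table 4; Stage 1 placebo is pooled as in SAP 6.2 (2 + 8 = 10).

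- Groups 7 and 8: 100/45 = 2.2 points
- Groups 4 and 5: 100/16 = 6.25 points
- Group 9: 100/15 = 6.7 points
- Pooled Stage 1 placebo: 100/10 = 10 points
- Groups 1 and 2: 100/4 = 25 points

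**Effect on the reported line when no fever was observed** (Clopper-Pearson 95%, the SAP's method):

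| n | 0 counted | 1 counted |
|---|---|---|
| 45 | 0% (0 to 7.9%) | 2.2% (0.06 to 11.8%) |
| 16 | 0% (0 to 20.6%) | 6.25% (0.2 to 30.2%) |
| 10 | 0% (0 to 30.8%) | 10% (0.3 to 44.5%) |

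At n = 45, two such participants give 4.4% (0.5 to 15.1%) and three give 6.7% (1.4 to 18.3%). These counts are assumed.

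**Illustration of frequency.** Assume each reading is missing independently with probability q. The documents give no value for q. The chance of at least one gap is 1 − (1 − q)^7 per dose and 1 − (1 − q)^21 over three doses. Expected numbers in a group of 45 with no true fever, under the 7.2.6 rows as written:

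| q (assumed) | Per dose | Over 3 doses |
|---|---|---|
| 0.5% | 3.4%, 1.6 participants | 10.0%, 4.5 participants |
| 1% | 6.8%, 3.1 | 19.0%, 8.6 |
| 2% | 13.2%, 5.9 | 34.6%, 15.6 |
| 5% | 30.2%, 13.6 | 65.9%, 29.7 |

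This ignores the group-level condition in 7.1.3 and any clustering of gaps within a participant. It shows how sensitive the line is and is not a forecast.

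**The case against.** The best defence is that the rows apply the last bullet of 7.1.3: flag neither Y nor N, systemic group Y, so missing days count in 'Any' but in no grade. That bullet covers every symptom, so temperature would not be a special case. This stands in part. But 7.2.6 leaves the condition out, and meeting it does not make an afebrile record a fever.

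A second defence is that only cards with all seven days recorded are analysed, so the partial case never arises. Read strictly, that empties every partly-missing row in the same table, for all symptoms. It adds a contradiction and does not resolve this one.

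Other points carry more weight:

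- Protocol 9.4 leaves missing-data procedures to the SAP, so the silence of SAP 3.3 (which lists only the Entered Set as a change) is weak evidence of an undeclared departure. The tension with Protocol 9.5 also reaches 7.1.3 generally, since 7.1.3 openly imputes for the 'Any' rows.
- If the tables show the UNKNOWN count, observed fever can be recovered by subtraction. The shells are not in the documents, so this cannot be settled.
- Counting unresolved temperatures as fever can be called conservative. The SAP does not label it a worst case, and it would raise placebo and control rates too.
- Simply switching to No while keeping these participants in the denominator treats them as non-events and could understate fever. That is why the fix needs a separate line.
- Reminder contacts, field-worker diary completion for illiterate participants and exclusion of unreturned diaries should keep gaps few.

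**Conclusion.** The concern holds: the two Temperature rows are wrong as written. Followed literally, they can leave the 'Any' fever line equal to or above observed fever, never below it, and they conflict with the SAP's own numerator and UNKNOWN rules.

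Each affected participant adds between 2.2 points (n = 45) and 25 points (n = 4). How many will be affected is not known and may be none. The conclusion assumes the rows are operative and that fever is flagged only from recorded values, as the table states. The CRF layout is not in the documents, so a fever reported without a usable reading cannot be ruled out.

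The reach is limited. The Grade 1 to 3 rows, the 0.5°C classes, fever above 40°C and holding rule 1d.2 all need a real value and are unaffected. A recorded No with fully missing readings is handled correctly, and no between-group safety tests are planned. This should be fixed before the final tables are programmed.

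**What to change.** 1. In the SAP 7.2.6 table, set the contribution to 'Any' to No for the two Temperature rows, unless a value of at least 38.0°C is observed or fever is explicitly marked as present on the CRF.
2. Report incomplete records without such a value on a separate unknown/incomplete line, so that they are not silently called afebrile.
3. If missing-as-fever is wanted, keep it only as a labelled worst-case sensitivity row.
4. Keep the 7.1.3 denominator. If participants with fully missing temperature are to leave it, amend the first bullet of 7.1.3 to say so.
5. Align the last bullet of 7.1.3 (for fever) and the complete-card sentence of 7.2.6 with the corrected table.

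The cost is SAP wording, a small change to the fever derivation and one extra table line. No new data are needed.

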7.2.7. GEOMETRIC MEAN CONCENTRATIONS (GMCs)/TITERS (GMTs)

Geometric Mean Concentration (GMC)/Titer (GMT) calculations are performed by taking the inverse logarithm of the mean of the log10 titer transformations. Antibody titers below the cut-off of the assay will be given an arbitrary value of half the cut-off of the assay for the purpose of GMT calculation. The cut-off value will be defined by the laboratory before the analysis.

8. OUTPUT PRESENTATIONS

The templates provided with this SAP describe the presentations for this study and therefore the format and content of the summary tables, figures and listings to be provided by IQVIA Biostatistics.

Some minor modifications may be necessary to the planned design of tables, figures, and listings to accommodate data collected during the actual study conduct.

9. DISPOSITION AND WITHDRAWALS

All participants who provide informed consent will be accounted for in this study. Participant disposition will be tabulated for each stage, each study treatment, and for all participants combined per stage and overall (using the Entered Set) with the number of participants who did not meet eligibility criteria, randomly assigned to treatment, completed Day X (for each scheduled visit), completed the study, prematurely discontinued, and the reason for early discontinuation. A listing will

Document: \\dccar2dnetvnasc01p-lan1.quintiles.net\cp_ops\PROJECTS\Glaxo SmithKline\GSK216152_WZA10802\SAP
 Author: PPD Version Number: 2.0
 Version Date: 07DEC2023

Template No: CS_TP_BS016 – Revision 7
 Effective Date: 01Nov2021

Reference: CS_WI_BS005

present dates of completion or early withdrawal and the reason for early discontinuation, if applicable, for each participant.

Listings of treatment discontinuation, participant visits, inclusion/exclusion criteria responses, study protocol deviations, treatment randomization and study treatment administration will be provided.

10. DEMOGRAPHIC AND OTHER BASELINE CHARACTERISTICS

Individual participant demographics and baseline characteristics (medical history and results from viral serology, HLA-B27 screening result and urine pregnancy tests) will be presented in listings.

Demographic characteristics such as age at first vaccination, sex, race (ethnic background), height, weight, and body mass index (BMI) will be summarized and tabulated for each treatment, each stage and for all participants overall. Descriptive statistics (mean, median and standard deviation) will be presented for age, height, weight, and BMI. Frequency counts and percentages will be presented for sex, race, and step.

No statistical testing will be carried out for demographic or other baseline characteristics.

11. PROTOCOL DEVIATIONS

11.1. DEVIATIONS RELATED TO STUDY CONDUCT

A deviation from a protocol occurs when Investigator site staff or a study participant does not adhere to the Protocol's stipulated requirements, whether inadvertently or planned. Protocol deviations will be listed and will include a classification of minor or major, as determined by study team.

Important protocol deviations will be reviewed by the study team to identify deviations which have the potential to affect the immunogenicity results.

11.2. DEVIATIONS RELATED TO IMMUNOGENICITY ANALYSIS

Changes to the procedures or events, which may impact the quality of the immunogenicity data, will be considered important protocol deviations and will be described within the clinical study report. These changes or events will include any circumstances that will alter the evaluation of the immunogenicity results. Examples include, but may not be limited to, sample processing errors that lead to inaccurate immunogenicity results, and/or inaccurate dosing.

Participants may be eliminated from the per-protocol set for analysis of immunogenicity if, during the study, they incur a condition that has the capability of altering their immune response or are confirmed to have an alteration of their initial immune status. Participants may also be eliminated

Document: \\dccar2dnetvnasc01p-lan1.quintiles.net\cp_ops\PROJECTS\Glaxo SmithKline\GSK216152_WZA10802\SAP
Author: PPD Version Number: 2.0
Version Date: 07DEC2023

Template No: CS_TP_BS016 – Revision 7
Effective Date: 01Nov2021

Reference: CS_WI_BS005

from the per-protocol set as described in Section 7.2 and Section 9.3 of the protocol. Such scenarios will be discussed by the study team and decision to exclude a participant and/or data from the Per-protocol analysis set (Day 29, Day 85 and Day 197) will be taken on a case-by-case basis.

Other deviations (not a comprehensive list) leading to elimination from the per-protocol set are:

- invalid informed consent
- fraudulent data
- randomization code broken
- dose volume insufficient
- vaccination not according to protocol
- vaccine dose storage conditions (temperature deviation)
- vaccine administered out of expiry date
- violation of inclusion/exclusion criteria
- interval between doses
- interval between post vaccination blood sampling and previous dose
- two doses not in the same treatment group
- concomitant infection related to study vaccine or not related to study vaccine that may alter the immune response
- serology result at post vaccination dose 2 not available for all assays (blood sample not available or result not available)

Protocol Deviation Management Plan (PDMP) describes the complete list of elimination codes that could lead to exclusion from the per-protocol set.

12. MEDICAL HISTORY

Medical History coded using MedDRA Version 26.0 or higher will be listed for the exposed set.

13. MEDICATIONS

Medication usage coded using the WHO Drug Dictionary Version GlobalC3Mar22 or higher will be listed for the exposed set.

‘Prior’ medications are medications which started and stopped prior to the first dose of study treatment.

‘Concomitant’ medications are medications which were taken during the treatment period, or

Document: \\dccar2dnetvnasc01p-lan1.quintiles.net\cp_ops\PROJECTS\Glaxo SmithKline\GSK216152_WZA10802\SAP
Author: PPD Version Number: 2.0
Version Date: 07DEC2023

Template No: CS_TP_BS016 – Revision 7
Effective Date: 01Nov2021

Reference: CS_WI_BS005

specifically:

- o started after the first dose of study treatment or
- o started prior to the first dose of study medication and were continued after the first dose of study treatment

The percentage of participants using concomitant medications (any medication, any antipyretic and any antipyretic taken prophylactically, respectively) during the 28-day follow-up period will be summarized by group after each vaccination and overall.

14. STUDY MEDICATION EXPOSURE

Exposure to study treatment as the number of doses administered will be presented for each treatment, each stage and all participants overall.

15. IMMUNOGENICITY ANALYSIS

The immunogenicity analysis will be based on the Per-protocol Set for analysis of immunogenicity. If, in any study group at any time point, the percentage of vaccinated participants with serological results excluded from the Per-protocol Set for analysis of immunogenicity is 10% or more, a second-line analysis based on the Full Analysis Set will be performed.

Numerical serology results will be derived from the content of IS.ISORRES in the SDTM dataset. For assays with a specific cut-off, the following derivation rules apply:

IS.ISORRES	Derived value
“NEG”, “-”, or “(−)”	cut-off/2
“POS”, “+”, or “(+)”	cut-off
“< value” and value is <= assay cut-off	cut-off/2
“< value” and value is > assay cut-off	value
“> value” and value is < assay cut-off	cut-off/2
“> value” and value is >= assay cut-off	value
“value” and value is < cut-off	cut-off/2
“value” and value is >= cut-off	value
All other cases	missing

Document: \\dccar2dnetvnasc01p-lan1.quintiles.net\cp_ops\PROJECTS\Glaxo SmithKline\GSK216152_WZA10802\SAP
Author: PPD Version Number: 2.0
Version Date: 07DEC2023

Template No: CS_TP_BS016 – Revision 7
Effective Date: 01Nov2021

Reference: CS_WI_BS005

The following derivation rules will apply in the context of LLOQ values:

- If baseline value is below LLOQ
 - 4-fold is defined as 4 times the LLOQ cut-off value
 - GMR is defined as within-participant GMR against LLOQ/2
- If baseline value is above or equal to LLOQ
 - 4-fold is defined as 4 times the baseline value
 - within-participant GMR is defined as within-participant GMR against the baseline value.

The following immunogenicity variables will be assessed:

Assay Type	Sampling Time Points	Component	Method	Unit of Measure	Number of Participants
Humoral Immunity (Antibody determination)	Stage 1: Days 1, 29, 57, 85, 169 and 197	Anti-S. Typhi Vi Ag total IgG	ELISA	EU/mL [#]	50 (Stage 1) 105 (Stage 2)
		Anti-S. Typhimurium O Ag total IgG		EU/mL	
		Anti-S. Enteritidis O Ag total IgG		EU/mL	

[figure not shown]
CCI

Document: \\dccar2dnetvnasc01p-lan1.quintiles.net\cp_ops\PROJECTS\Glaxo SmithKline\GSK216152_WZA10802\SAP
 Author: PPD Version Number: 2.0
 Version Date: 07DEC2023

Template No: CS_TP_BS016 – Revision 7
 Effective Date: 01Nov2021

Reference: CS_WI_BS005

CCI

The IgG against Vi antigen will be determined using GVGH ELISA and the results will be presented in EU/mL unit, which may be further converted to µg/mL, based on correlation with concentration of the standard calibrated against the international standard/another standard already calibrated.

A listing of collection dates and times for the immunogenicity variables will be presented for participants within each treatment group. For each component, the concentration/titer will be listed and summarized by treatment groups across all scheduled timepoints during entire study for each stage. Antibody concentrations/titers for all components will be investigated using Reverse Cumulative Distribution Curves based on the Per-protocol analysis set.

For each study group, each stage, at each timepoint that blood samples are collected for humoral immune response and for each component as measure by ELISA and CCI

- Geometric mean concentrations/titers and their 95% CI will be calculated.
- Within-participant geometric mean ratio (geometric mean at 28 days after each study intervention to each study intervention administration baseline, ie, Day 29 versus Day 1, Day 85 versus Day 57 and Day 197 versus Day 169 and to Day 1 baseline) with their 95% CI will be tabulated.
- Percentage of participants with ≥ 4 fold-increase from Day 1 baseline with their exact 95% CI will be calculated.
- Unadjusted between-group ratio of GMC with 95% CI between iNTS-TCV groups and iNTS-GMMA and TCV groups will be computed for each anti-serotype specific IgG^{1*}, visit, and administration. The unadjusted ratios for each visit will be calculated using results from the corresponding visit as the dependent variable and the treatment group as independent variable. No other covariates will be included in the model.

For each study group, each stage, at each timepoint for S. Typhi Vi component as measured by ELISA:

- The number and percentage of participants with Anti-S. Typhi Vi Ag IgG antibody concentrations \geq CCI and their 95% exact CI will be calculated.
- The number and percentage of participants with Anti-S. Typhi Vi Ag IgG antibody

¹ * Anti- Salmonella Typhi (S. Typhi) Vi antigen (Ag) total IgG, Anti Salmonella Typhimurium (S. Typhimurium) O Ag total IgG, Anti Salmonella Enteritidis (S. Enteritidis) O Ag total IgG will be tested.

concentrations \geq [CC1] and their 95% exact CI will be calculated.

The above tabulations may be performed by LLOQ status at baseline (above or equal to cut-off versus below the cut-off) for all 3 components, data permitting.

Only for S. Typhi Vi component the above tabulations may be performed by Anti-S. Typhi Vi Ag IgG antibody concentrations status at baseline as measured by ELISA ($>=$ [CC1] and $<=$ [CC1], $>=$ [CC1] and $<=$ [CC1]), data permitting.

Linear mixed model with repeated measures (MMRM) will be used to perform pairwise comparison between full doses of iNTS-TCV and iNTS-GMMA + TCV at Day 29, Day 57, Day 85, Day 169 and Day 197. The model will use fixed effects for center, treatment, time point, treatment*time point, center*treatment, baseline immunogenicity value as covariate, and a repeated time point effect within a participant under an unstructured covariance matrix. Variance between the groups will not be considered equal unless the assumption leads to convergence issues. Additional covariance structures and suitable transformation (e.g., log) may be explored to attain convergence and meet model assumptions, respectively. This analysis will be performed for full doses of iNTS-TCV and iNTS-GMMA + TCV from both the stages.

```
proc mixed data=indsn;  by parameter;  
  class subjid center trta avisit;  
  model aval=center trta avisit trta*avisit center*trta baseline/ddfm=satterth;  
  repeated avisit/subject=subjid type=un group=trta;  
  lsmeans trta*avisitn/pdiff cl alpha=0.05;  
  run;
```

In this analysis, immunogenicity data from full dose group in Europe will be pooled with those from full dose group in Africa if p-value associated to parameter for center*treatment interaction from MMRM model ≥ 0.10 (i.e., suggesting that impact of treatment on immunogenicity endpoint does not depend on center). In that case, GMC, GMRs, and ratio of GMC will be calculated for entire full dose group (i.e., Europe + Africa) adjusted by center from the above MMRM model without the center*treatment interaction term.

In case center*treatment interaction term is significant (i.e., p-value <0.1) the following analyses will be performed: 1) main analysis including center*treatment interaction term and GMC ratio separately for Europe and Africa will be produced from model with center*treatment interaction term, 2) sensitivity analysis excluding center*treatment interaction and GMC ratio for pooled Europe and Africa will be produced from model without center*treatment interaction term.

The following Table summarizes the statistical analyses:

Document: \\dccar2dnetvnasc01p-lan1.quintiles.net\cp_ops\PROJECTS\Glaxo SmithKline\GSK216152_WZA10802\SAP
Author: PPD Version Number: 2.0
Version Date: 07DEC2023

Template No: CS_TP_BS016 – Revision 7
Effective Date: 01Nov2021

Reference: CS_WI_BS005

Starting Model	P-value for Center*Treatment Interaction	Main Analysis Model	Sensitivity Analysis
center, treatment, center*treatment	≥0.1 drop center*treatment from the model	Starting model without center*treatment term	No sensitivity analysis
time point, treatment*time point, baseline immunogenicity value as covariate	<0.1	Same as the starting model. Output GMC ratio from model with interaction, separately from Europe and Africa	Starting model without center*treatment term

In other words, analysis pooling Europe and Africa data adjusting treatment effect for center variable will be performed in all cases, however in case center*treatment interaction parameter is statistically significant at 0.1 level, it will be considered as sensitivity analysis.

A sensitivity analysis may also be performed pooling Europe and Africa and adjusting treatment effect for race variable if there is evidence of different races at the two centers.

CCI

